#### *Monitoring of the intervention*

The study will be monitored by the study investigator(s). Based on conversations with our Clinical Advisory Board and prior studies, we expect very few people to become hypercalcemic due to study medication. The PI(s) will also conduct an interim analysis of COVID-19 incidence among the two study arms approximately 6 months into the study to determine study continuation in addition to routine safety review.

#### Data and Safety Monitoring Board (DSMB) Charter

##### *Trial Monitoring*

The trial will be monitored by an independent Data and Safety Monitoring Board for this study made up of three members of the UC BSD faculty with experience in clinical trial management and expertise in critical care, pulmonology, and biostatistics. The DSMB members are: [name], DSMB Chair, [name], and [name].

##### *Monitoring Frequency*

The DSMB will meet to review initial laboratory values and quarterly thereafter to review the overall protocol administration, review adverse events, and trends in laboratory values for determination of safe progression of the study. DSMB members will schedule additional meetings as needed to review adverse events.

##### *Adverse Event Management*

Adverse Events, Serious Adverse Events and Unanticipated Problems will be reported to members of DSMB by the PI immediately for independent review. These events will be managed by the PI and Co-Investigator at the direction of the DSMB and UChicago Medicine Biological Sciences Division Institutional Review Board.

#### XII. Payment to subjects:

**XIII. Procedures to obtain and record informed consent:**

After completing the eligibility questionnaire on the REDCap page, participants will be redirected to the electronic consent form which they'll have to complete prior to beginning the baseline survey. Participants will also be informed that the electronic consent form will cover all subsequent study participation. The electronic consent form will detail the voluntary nature of participating in the research, procedures, potential risks as well as our prepared measures and protocols to maintain their confidentiality. In the consent form, subjects will be informed that they will be receiving a daily dose of vitamin D, either low or moderate, and must self-administer this dose each day and that they are blinded to the dose they receive. The consent form will also ask participants if they are interested in the at-home blood testing for Vitamin D levels and COVID-19 antibodies at the beginning or end of the study. There is no consequence for opting out of the blood tests.

When participants have read through the consent form, they will indicate their consent by signing their name and entering the current date and time. If they do not consent, they may simply exit the page. When a participant chooses to consent to the study, a signed PDF copy of their eConsent form will be automatically emailed to them upon completion with the following text: "Thank you for consenting to participate in the study. Attached is a copy of the consent form you signed, which you may keep for your personal records. If you would like a copy that includes the investigator's signature, please email us at [[contact]](mailto:[contact])." After consenting, subjects will be redirected to begin the baseline survey. Once a subject finishes the baseline survey, the research team will reach out to them to confirm next steps, as well as whether the subject is ready or not to receive test kit(s) should they have consented to optional vitamin D level and/or COVID-19 antibody testing. This communication step both ensures any optional testing is readily performed before vitamin D is sent to subjects and to avoid further delays before vitamin D is sent.

**XIV. Procedures to maintaining confidentiality:**

Health Lab has strict data security and confidentiality procedures in place as described below. All research staff are required to sign a confidentiality pledge and to complete human subject's research training. Moreover, the data will be stored on a firewall protected, restricted access server that is only accessible to select Health Lab researchers. Additionally, the survey data will be collected through University of Chicago's REDCap system which meets all HIPAA requirements for data security. For the potential risks relating to vitamin D toxicity and insufficiency, we think these are very low but will inform participants of them prior to their participation in the study.

Furthermore, participants will be given a contact number and email address for study staff and encouraged to monitor for and report any possible signs of vitamin D toxicity, and to report any COVID-19 symptoms or positive tests. Participants will also be given instructions for any home testing-related risks such as bruising or bleeding risk. Participants will be advised to seek medical care immediately for any problem they view as urgent and the PI will be informed within 24 hours. In the event of an unanticipated problem, study staff will inform the PI within 24 hours, and document study protocol number, participant's initials, date of event, and description of event. Study staff will then formally submit an "Unanticipated Problem Event Form" to the UChicago Biological Sciences Division IRB within 5 days.

---

## **XVI. Description of recruiting methods:**

Script from end of NIH study for transitional subjects  
Recruitment from NIH pool

Given the current risk of COVID-19, we will use virtual recruiting as much as possible. Recruitment information will vary by partner, but recruitment materials and emails will have links to the research website for additional information and enrollment. On the website, interested participants will complete a 2-minute eligibility questionnaire to determine their eligibility for the study. Persons reporting health conditions indicating risk from vitamin D treatment (hypercalcemia, hyperparathyroidism, some medications, kidney stones, pregnancy, lactation) or an allergy to Vitamin D will be ineligible. Eligible participants will be guided to a secure REDCap website where they will complete a consent form and a 15-minute baseline survey that asks about demographics, health and health behaviors (including vitamin D intake and sun exposure), and COVID-19 risks. We plan to recruit 20% (200 participants) of the eligible participants at the beginning of the study to receive and complete a vitamin D level and a COVID-19 anti-body test at their places of residence. At the end of the study, all study participants will be offered an at-home COVID-19 antibody test kits. Participants will have the option to opt in or out of these tests on the study consent form.

We will also operate a telephone line staffed by our research staff on which potential participants can have questions answered and assistance with assessing eligibility and complete the online intake survey. Study recruitment will take place within the first 2 months of the study period. Though our primary recruitment approaches will be virtual, the community partners will also hang posters and flyers throughout their agencies.

Health Lab researchers and analysts will monitor survey completion at each wave and send out email and telephone reminders to subjects who have not completed the survey.

#### **XVII. Notification of primary physician:**

Subjects' primary care physicians will not be notified of subjects' involvement in the proposed research. One exception to this is if a subject is counseled to seek care from their primary care physician due to an abnormal laboratory result or symptom as described above.

#### **XIX. Pregnancy test**

Subjects will not be asked to take a pregnancy test before or during the study. We will ask potential subjects during recruitment screening to self-report pregnancy. If a potential subject self-reports pregnancy, they will be excluded as noted above. Upon enrollment, subjects will be asked to inform the study team if they become pregnant during the study.

#### **XX. Rationale for excluding women/minorities and/or children:**

We will not recruit those who are considered special populations. We are excluding pregnant and breastfeeding women because they have unique guidelines for supplementation and to protect the fetus and infants. We are excluding children, prisoners, and neonates due to the study design and study population.

#### **XXI. Unblinding protocol**

At the end of the intervention period for all participants in this protocol, we will unblind participants to their vitamin D dose assignment as detailed in "Dose Unblinding Email". We will do this at the end of the intervention for all participants because we, as the study team, are blinded to dose assignments until the end of the intervention period for all participants.

#### **XXII. Notification of Publication**

Upon publication of results related to this study, we will notify all participants in this protocol of the availability of these results. In that correspondence, we will attach the most-final version of the publication as allowed by the publisher.

**APPENDIX A: Virtual consent method**

1. Once interest has been expressed and the individual has been screened for eligibility in the REDCap intake form, the subject will be redirected to an electronic consent form. For transitional NIH study participants, eligibility will be affirmed on the consent form. Participants that have graduated from the NIH study prior to the approval of this amendment (amendment #24 for #IRB20-0847), will be considered new participants and will complete the same eligibility screening, consent, and baseline survey process as other new participants
2. After a subject has opened the electronic consent form, the subject will read through the form, which will detail the voluntary nature of participating in the research, procedures, potential risks as well as our prepared measures and protocols to maintain their confidentiality.
3. When participants have read through the consent form, they will indicate their consent by signing their name and entering the current date and time. If they do not consent, they may simply exit the page.
4. When a participant chooses to consent to the study, a signed PDF copy of their eConsent form will be automatically emailed to them upon completion.
5. Within three working days, a Health Lab RC/RA will review to make sure consent form is valid.

Primary Outcome Measure

Title: Time from randomization to first participant-reported COVID-19 infection.

Description: Reported in a post-randomization survey.

Time frame: From date of randomization to the earliest of either the first participant-reported COVID-19 infection up to and including 365 days after randomization or right censoring up to 365 days after randomization. Censoring events include (1) the last date of a completed post-randomization survey if no post-randomization surveys report COVID-19 infection and the completion date of the last post-randomization survey was \leq 365 days after randomization, (2) 365 days after randomization if no post-randomization surveys report COVID-19 infection up to and including 365 days after randomization and the completion date of the last post-randomization survey was $>$ 365 days after randomization, or (3) date of study withdrawal.

Primary analysis: We will use a multivariable Cox proportional hazards regression model to estimate an adjusted hazard ratio of the effect of moderate versus low dose vitamin D on the outcome. Covariates will include age, sex, race and ethnicity, baseline sun exposure, baseline insomnia severity, baseline COVID-19 exposure outside work, baseline employment, randomization date, and baseline geographic location. The selection and coding of these covariates mirror a prior NIH-funded trial of vitamin D and COVID-19 (NCT04868903). Coding of these covariates include age (continuous), sex (male versus female), race and ethnicity (non-Hispanic White versus non-White or Hispanic), sun exposure (average \leq 30 minutes per day versus $>$ 30 minutes per day), insomnia severity (no or subthreshold insomnia versus moderate or severe insomnia), COVID-19 exposure outside work (no versus yes), and employment (no versus yes). Non-Hispanic White participants will be defined as those who report White race and non-Hispanic or Latino ethnicity. Non-White or Hispanic participants will be defined as those who report either non-White race or Hispanic or Latino ethnicity. Whereas recruitment in the NIH trial was limited to Chicagoland and stratified by recruitment site (UChicago Medicine and Rush University Medical Center), this study recruited participants across the United States, such that we will include baseline geographic location as a covariate, defined by baseline mailing address latitude $<$ 40.0 or \geq 40.0 degrees. Furthermore, whereas the NIH trial recruited participants who concluded their participation prior to when Omicron arrived in Chicago about December 1, 2021, every participant in this study could be active in the study after Omicron arrived in the United States about December 1, 2021. Rather than control for randomization date with a linear time trend and an indicator variable for potential participation after Omicron arrived like the NIH trial, we will control for randomization date with a series of thirteen quarters defined by calendar quarter and year (Q1 2021 [December 2020 through March 2021], Q2 2021 [April 2021 through June 2021], Q3 2021 [July 2021 through September 2021], Q4 2021 [October 2021 through December 2021], Q1 2022 [January 2022 through March 2022], etc. up to Q1 2024 [January 2024 through April 2024]).

Secondary analysis of non-Hispanic White participants living north of 40.0 degrees: We will use a multivariable Cox proportional hazards regression model to estimate an adjusted hazard ratio of the effect of moderate versus low dose vitamin D on the outcome in participants who are non-Hispanic White and whose baseline mailing address latitude is \geq 40.0 degrees. Covariates will mirror those described in the primary analysis, excluding race and ethnicity and baseline geographic location. We prespecify this secondary analysis prior to unblinding because

the NIH trial cited above found stronger evidence of increased time to first COVID-19 infection with vitamin D supplementation among non-Hispanic White participants, and participants in that trial were recruited in the Chicagoland area which has a latitude north of 40.0 degrees. The NIH trial also found stronger evidence of increased time to first COVID-19 infection with vitamin D supplementation among participants who reported an average of ≤ 30 minutes of sun per day.

Additional Analyses

Time-varying analysis: We will use a time-varying, multivariable Cox proportional hazards regression model to estimate an adjusted hazard ratio of the effect of moderate versus low dose vitamin D in each calendar quarter (Q1: January through March, Q2: April through June, Q3: July through September, Q4: October through December) on the outcome in participants whose baseline mailing address latitude is ≥ 40.0 degrees. Covariates will mirror those described in the primary analysis, with the addition of four calendar quarter indicator variables as time-varying covariates. Furthermore, instead of using a single indicator variable for moderate dose vitamin D, we will include four indicator variables for treatment with moderate dose interacted with the time-varying calendar quarter. The reference group for the uninteracted and interacted time-varying calendar quarter indicator variables will be Q1 for low dose vitamin D.

Treatment heterogeneity analysis: We will use a multivariable Cox proportional hazards regression model to estimate an adjusted hazard ratio of the effect of moderate versus low dose vitamin D on the outcome in every subgroup of participants defined by the covariates in the primary analysis, except for the thirteen quarters defined by calendar quarter and year. Age will be dichotomized as <45 or ≥ 45 years. We will also analyze subgroups of Blacks or African-Americans, non-Whites or Hispanics with baseline mailing address latitude ≥ 40.0 degrees, non-Whites or Hispanics with baseline mailing address latitude <40.0 degrees, non-Hispanic Whites with baseline mailing address latitude <40.0 degrees, participants unimmunized for COVID-19 at baseline, and participants fully immunized for COVID-19 at baseline. Full immunization refers to one vaccine dose from Johnson & Johnson or two vaccine doses from other manufacturers.

Additional outcomes: We will analyze COVID-19 infection severity for moderate versus low dose vitamin D as measured by rates of symptoms using a modified Beat COVID-19 instrument (NCT04337762), hospital admission, hospitalization with ICU admission, hospital length of stay, whether ventilator, high-flow nasal oxygen, or helmet-based ventilation is used, and death.

Other Statistical Considerations

Proportional Hazards Assumption: In the primary analysis, secondary analysis of non-Hispanic White participants living north of 40.0 degrees, time-varying analysis, and treatment heterogeneity analysis, the proportional hazards assumption will be assessed using the *estat phtest* command in Stata with rejection of proportion hazards defined by $p < 0.05$ for any variable or the global test, or by visual assessment of Schoenfeld residuals. Continuous variables which fail proportional hazards will be categorized. For any categorical variable or categorized continuous variable which fail proportional hazards, we will perform Cox regression which stratifies based on that variable. If the moderate dose vitamin D variable fails the proportional hazards assumption, we will estimate non-proportional hazards models.

Missing Data: Assuming missingness at random, we will impute missing values of covariates with multiple imputation by chained equations with 20 imputations. Covariates in the imputation will include the covariates in the primary analysis excluding moderate dose vitamin D. The imputation for the secondary analysis of non-Hispanic White participants living north of 40.0 degrees and the treatment heterogeneity analysis will be performed among the denominator of all participants in the primary analysis.

Statistical Significance and Multiple Testing: Statistical significance will be determined by $p < 0.05$ for the primary analysis and the secondary analysis of non-Hispanic White participants living north of 40.0 degrees with no adjustment for multiple comparisons.

Software: Data analysis will be executed in Stata 18.0.

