We estimate statistical power using a simulation model based on conservative estimates of the fraction of Chicagoans already immune but unaware they have had COVID-19 ( $\leq 10\%$ ), monthly incidence of COVID-19 (3%/month for Black and Latinx persons and 1%/month for White persons), size of the true effect of vitamin D on incidence we seek to assess, confidence we wish in that assessment, and length of time participants are followed. Based on this we propose to recruit at least 2,000 participants, yielding 80% power at  $p < 0.05$  to demonstrate a reduction of 20% or more in COVID-19 incidence due to vitamin D within 12 months of randomization.

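### The SAP's treatment heterogeneity analysis plans a separate hazard ratio in each subgroup and no dose-by-baseline-factor contrast, so it does not estimate whether effects differ between groups

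*SAP*

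**What the plan says.** The SAP's Treatment heterogeneity analysis will "estimate an adjusted hazard ratio of the effect of moderate versus low dose vitamin D on the outcome in every subgroup of participants". The subgroups are defined by the primary covariates, apart from randomization quarter. With age dichotomized, that is eight two-level factors, or 16 subgroups. Six more are added, making 22: Black or African-American participants, three race-by-latitude cells, and two groups by immunization status at baseline.

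The secondary analysis is also a within-group HR, in non-Hispanic White participants at latitude 40.0 or above: "Covariates will mirror those described in the primary analysis, excluding race and ethnicity and baseline geographic location". Its rationale is that an earlier trial "found stronger evidence of increased time to first COVID-19 infection with vitamin D supplementation among non-Hispanic White participants".

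The SAP writes out an interaction where it wants one. In the Time-varying analysis, "we will include four indicator variables for treatment with moderate dose interacted with the time-varying calendar quarter". That concerns calendar time, not a baseline factor, and is confined to participants at latitude 40.0 or above. The Cox models in Protocol sections III and IX list covariates but no dose-by-covariate term.

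Under Missing Data: "Covariates in the imputation will include the covariates in the primary analysis excluding moderate dose vitamin D". The outcome is not listed there, and the same imputation serves the subgroup analyses.

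**The concern.** Heterogeneity is a statement about the difference between two effects. A set of HRs, each with its own interval, does not give that difference or its uncertainty. The usual substitute is to note which subgroups are significant, and that is unreliable because each subgroup has limited power of its own.

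The earlier trial's finding makes the comparison a natural one to draw from this trial. Without a planned contrast, any comparison would be chosen after 22 HRs have been seen.

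Two details make a later contrast harder. First, the immunization groups are "participants unimmunized for COVID-19 at baseline, and participants fully immunized for COVID-19 at baseline", and "Full immunization refers to one vaccine dose from Johnson & Johnson or two vaccine doses from other manufacturers". Someone with one dose of a two-dose product is in neither group. The Black or African-American subgroup likewise has no stated comparator. Second, a factor imputed without regard to dose and outcome carries no information about the dose effect in the imputed records, which draws the subgroup HRs together.

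**Working it through.** **Plan's own figure.** The SAP gives none for this analysis. The protocol states 80% power for a 20% reduction with 2,000 participants. A two-sided log-rank test needs 631 events (Schoenfeld) for HR 0.80, and the protocol's rates give 185 to 559 events depending on ethnic mix and immune fraction. The mix is not stated, so the 80% is neither confirmed nor refuted. The point does not depend on it.

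**Event totals (illustrative).** Inputs from Protocol section III: "monthly incidence of COVID-19 (3%/month for Black and Latinx persons and 1%/month for White persons"; at most 10% already immune; 12 months; 1,000 per arm. Assumed: 33% or 50% White, a 20% cut in the monthly hazard, and 0% or 20% of events lost (a bound suggested by the 80% follow-up target in Protocol section IV).

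Risk = 0.9 × [1 − (1 − inc × h)^12], with h = 1 or 0.8:
- Black/Latinx: 0.2755 and 0.2276, sum 0.5031
- White: 0.1023 and 0.0827, sum 0.1850
- One-third White: 667 × 0.5031 + 333 × 0.1850 = 335.4 + 61.7 = 397 events, 15.5% of them in White participants
- 50% White: 500 × 0.5031 + 500 × 0.1850 = 251.6 + 92.5 = 344 events, 26.9% in White participants
- With 20% of events lost: 318 and 275

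**Exactly one of two levels significant when both true HRs are 0.80.** With d events in a level, the mean of Z is 0.2231 × √d / 2. If the two levels have power a and c, the probability is a(1 − c) + c(1 − a).
- 275 events, 50:50: mean 1.308, power 0.258 in each; 2 × 0.258 × 0.742 = 0.383
- 275 events, 30:70: 0.396
- 397 events, 50:50: 0.455
- 397 events, 30:70: means 1.218 and 1.860, powers 0.230 and 0.460; 0.230 × 0.540 + 0.460 × 0.770 = 0.478

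The range is about 38% to 48%. A single interaction test at 0.05 rejects in 5% of trials by construction.

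**Power of the contrast.** SE of the log ratio of HRs = √(4/d1 + 4/d2). The ratio detectable with 80% power is exp(−2.80 × SE).

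| Events | Split | SE | Power, ratio 0.80 | Detectable ratio |
|---|---|---|---|---|
| 275 | 50:50 | 0.241 | 0.152 | 0.51 |
| 275 | 30:70 | 0.263 | 0.136 | 0.48 |
| 397 | 50:50 | 0.201 | 0.199 | 0.57 |
| 397 | 30:70 | 0.219 | 0.175 | 0.54 |

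For the secondary subgroup against all others, the White event share stands in for the subgroup's share. Power is 0.127 (397 events, 15.5%), 0.111 (318, 15.5%), 0.151 (344, 26.9%) and 0.130 (275, 26.9%). These are optimistic, because only some White participants are non-Hispanic and at latitude 40.0 or above.

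**Multiplicity.** Eight factors, the joint race-by-latitude group, Black race and immunization make 11 tests. If they are independent and no effects differ, 1 − 0.95^11 = 0.43.

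**Imputation.** Suppose a share m of a factor's values is missing completely at random and is imputed without dose or outcome, with the other covariates uninformative. The log ratio then shrinks by about (1 − m). With log 0.80 = −0.223, a true ratio of 0.80 becomes exp(−0.223 × 0.95) = 0.809 at 5% missing, 0.818 at 10% and 0.837 at 20%.

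A simulation (prevalence 50%, hazard 0.25 per year, three runs of 4 million, full-data ratio 0.802) gave these ratios at 5%, 10% and 20% missing:
- Neither dose nor outcome in the imputation: 0.812, 0.821, 0.839
- Dose, event indicator and cumulative hazard as main effects only: 0.812, 0.821, 0.838
- With dose × event and dose × cumulative-hazard terms added: 0.803, 0.803, 0.802

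Main effects alone therefore do not remove the attenuation.

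**The case against.** The strongest reply is that little is missing. Both levels of all eight factors are planned. The secondary analysis and the heterogeneity section together cover all four race-by-latitude cells, so ratios of HRs for disjoint groups follow from the planned estimates and standard errors. This stands as far as feasibility goes: the gap is in what is prespecified, not in what the data allow.

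Second, the 38% to 48% figure uses a per-subgroup p<0.05 rule that the SAP does not set. Its significance rule covers only the primary and the one secondary analysis. This also stands. A reader might infer that the plan will declare false subgroup differences at that rate; the documents do not support that. The figure shows only why counting significant subgroups is a poor substitute for a contrast.

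Third, the imputation effect may be very small. The baseline survey is a condition of enrollment for new participants, transitional participants had recently answered the same questions, and latitude comes from the mailing address. The missing share is not given. A shift from 0.80 to between 0.81 and 0.84 is minor beside a standard error of 0.20 or more on the log scale. This stands, so imputation is a secondary matter.

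Fourth, interaction tests bring low power and their own multiplicity. Both are true. They argue for intervals and an exploratory label, not for leaving the contrast out.

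**Conclusion.** The concern holds as a gap in prespecification: the analysis named for heterogeneity does not estimate it. The textual finding rests on no assumption. The sizes do, namely on assumed event totals, splits, White share and loss: about 38% to 48% discordant significance under a common HR of 0.80, and power of about 14% to 20% for a ratio of 0.80 (11% to 15% for the secondary subgroup).

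Three stronger readings are not supported. The secondary analysis is not invalid; it is a proper within-group estimate for its stated population, though alone it cannot show an effect specific to that group or stronger there. The SAP does not itself claim such a difference; it reports the earlier trial's result as its reason for looking. The imputation range of 0.81 to 0.84 is not an upper bound, because it assumes values missing completely at random, whereas the SAP assumes only missingness at random. The point leaves the primary analysis untouched.

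**What to change.** In the SAP's Treatment heterogeneity analysis:

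- For each baseline factor, add one full-sample Cox model with the primary covariates, the factor's main effect as coded for the subgroups, and a dose × factor term. Report the ratio of HRs with its 95% interval beside the subgroup HRs. Note that it need not equal the quotient of the separately fitted HRs, because covariate effects are shared.
- Do the same for non-Hispanic White at latitude 40.0 or above against all others, for Black or African-American race against all others, and for baseline immunization, with partly immunized participants as their own level or explicitly excluded.
- Label these analyses exploratory. State that about 11 tests are unadjusted, with about a 43% chance of at least one p<0.05 under no heterogeneity if they are independent. Base any statement that effects differ on the ratio and its interval, not on which subgroups are significant.
- If factors have missing values, impute for these models separately by arm with the event indicator and cumulative hazard included, or include dose × event and dose × cumulative-hazard terms. Include Black race and immunization if they have missing values.

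The cost is SAP wording, one extra model per factor and a second imputation model, with no new data. The downside is low power: 80% power needs a ratio of about 0.48 to 0.57. A non-significant interaction must be shown with its interval and not read as equal effects.

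### Baseline COVID-19 immunization defines two SAP subgroups but is not in the primary Cox model; adding it is an optional, small efficiency gain

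*SAP*

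**What the plan says.** **Primary model.** The SAP (Primary analysis) lists the adjustment set: "Covariates will include age, sex, race and ethnicity, baseline sun exposure, baseline insomnia severity, baseline COVID-19 exposure outside work, baseline employment, randomization date", plus latitude of the mailing address. Immunization is not among these nine. The stated reason for the list is that it mirrors an earlier NIH-funded trial. The SAP departs from that trial twice, for geography and for randomization date, and explains each departure by a difference in design or timing. Randomization date enters as thirteen calendar quarters, from December 2020 to April 2024.

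**Subgroups.** The SAP (Treatment heterogeneity analysis) adds subgroups of "participants unimmunized for COVID-19 at baseline, and participants fully immunized for COVID-19 at baseline". It defines full immunization by number of doses and manufacturer. It assigns no place to people with some doses but fewer than that.

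**Imputation.** The SAP (Missing Data) imputes with the primary-model covariates only, so immunization is not in the imputation model.

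**Protocol.** Neither covariate list (sections III and IX) names vaccination, but the list in section IX is expressly not exhaustive. No section lists a vaccination item in the baseline survey; that the variable is held is an inference from the planned subgroups.

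**The concern.** Entry spans more than three years of the pandemic, so immunization status probably differs between participants. A quarter term compares people who entered at the same time. It removes differences in average uptake between quarters but cannot separate immunized from unimmunized people within one. If immunization predicts reported infection, leaving it out of a Cox model has two consequences: the estimated dose hazard ratio moves slightly towards 1, and any chance imbalance in immunization between the arms stays in the estimate. At stake is a little power, in a trial whose stated inputs leave none to spare on the hazard-ratio scale.

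**Working it through.** **1. The plan's power figure, as context.** Protocol section III gives a minimum of 2,000 recruits, 80% power at the 0.05 level, and a target effect worded as follows: "to demonstrate a reduction of 20% or more in COVID-19 incidence due to vitamin D within 12 months of randomization". The assumed infection rates are "3%/month for Black and Latinx persons and 1%/month for White persons". There is also an allowance of at most 10% for the "fraction of Chicagoans already immune but unaware they have had COVID-19". That allowance concerns past infection; vaccination is not an input. The SAP has "Statistical significance will be determined by $p < 0.05$ for the primary analysis"; I take it as two-sided. The racial mix is not stated.

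Events needed for HR 0.80 (Schoenfeld): 4 × (1.960 + 0.842)² / (ln 0.80)² = 631.

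Events expected with 75% Black/Latinx (assumed), no immune fraction and 1,000 per arm:
- Low dose: 0.75 × (1 − 0.97¹²) + 0.25 × (1 − 0.99¹²) = 0.258.
- Moderate dose, monthly rates × 0.8: 0.75 × (1 − 0.976¹²) + 0.25 × (1 − 0.992¹²) = 0.213.
- Total: about 471 events.
- Power: Φ(√(471/4) × 0.223 − 1.960) = 68%.

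For 50% to 100% Black/Latinx, with 0% or 10% immune and before losses, events run from 344 to 559 and power from 54% to 75%. Read instead as a 20% cut in 12-month risk, power is 61% to 87%. The stated 80% can therefore be neither confirmed nor refuted.

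**2. Why the standard error does not fall.** In a 1:1 Cox comparison SE(log HR) ≈ 2/√D, so 2/√471 = 0.092. It depends on the number of events, which a covariate does not change.

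**3. Simulation with and without immunization.** Settings: n = 2,000, 1:1, 12 months, true dose HR 0.80, 75% Black/Latinx, average incidence held at the protocol's level. Assumed: immunization HR 0.7, 0.5 or 0.3, with uptake rising from 5% to 90% over six recruitment blocks. Both models include race and block terms (500 trials per row).

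| Immunization HR | Dose HR without → with | SE without → with | Mean z without → with | Power without → with |
|---|---|---|---|---|
| 0.7 | 0.802 → 0.801 | 0.0930 → 0.0930 | −2.373 → −2.378 | 68.4% → 68.8% |
| 0.5 | 0.805 → 0.803 | 0.0936 → 0.0937 | −2.310 → −2.343 | 65.4% → 66.6% |
| 0.3 | 0.806 → 0.801 | 0.0949 → 0.0950 | −2.272 → −2.337 | 61.0% → 64.8% |

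The gains are 0.4, 1.2 and 3.8 points, with Monte Carlo error of roughly 1 point. Converting mean z in the last row gives Φ(0.312) = 62.2% and Φ(0.377) = 64.7%, a gain nearer 2.4.

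With a race term only (1,000 trials), the gain at HR 0.3 was 5.2 points at 50% uptake (dose HR 0.806 → 0.798) and 4.3 at 80%. At HR 0.5 it was 1 to 2 points. A separate simulation with thirteen entry quarters and calendar waves gave 66.0% → 67.2% at HR 0.5 and 57% → 62% at HR 0.3.

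**4. No dose effect.** With a true dose HR of 1.0, rejection rates were 4.2% to 6.2% across both models. The omission does not inflate type I error.

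**5. Chance imbalance.** At 50% uptake the between-arm difference in proportion immunized has SD √(4 × 0.5 × 0.5 / 2,000) = 0.022. Multiplying by |ln 0.5| = 0.693 or |ln 0.3| = 1.204 gives a shift in log HR of about 0.016 or 0.027. The thirteen-quarter simulation gave 0.019 to 0.032, or 0.2 to 0.3 of the SE.

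**The case against.** The strongest case for leaving the model alone has four parts.

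- **The list has a reason.** Matching the earlier trial keeps the two results comparable. That is a legitimate choice. But the SAP already departs from the list where circumstances changed, and protocol section IX leaves room for additions.
- **The quarters do much of the work.** True for differences between quarters. The documents do not say how much variation remains within them, and the gains in the table are what is left after block terms.
- **Chance imbalance is ordinary sampling variation.** The reported SE and type I error already cover it. This stands: adjustment improves the single estimate but repairs no error.
- **The gain rests on assumptions.** At HR 0.7 it is about nil, and only HR 0.3 gives a clearly visible gain. Baseline status can also change during 12 months of follow-up, so a simulation with a constant effect is nearer a best case. This stands too.

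A reader might infer three stronger things, and the documents support none of them. One is that precision is being given away; the SE does not change. Another is that immunization is a strong risk factor in this cohort; no section gives a vaccine effect or uptake.

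The third is that the primary comparison is confounded. Randomized allocation rules that out. Transitional participants do keep their earlier arm, and two of three earlier arms map to 4,000 IU (protocol sections III and VII). A systematic imbalance there would require their immunization to differ from that of new entrants in the same quarter, and the documents give neither that difference nor their number. As illustration, assume equal earlier arms (2:1 allocation), a transitional share of 10% to 20%, a 30-point difference in immunization and HR 0.5. The between-arm difference in transitional share is then 0.060 to 0.107. Multiplied by 0.30 × 0.693, this shifts the log HR by 0.012 to 0.022 before quarter adjustment, against an SE near 0.093.

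**Conclusion.** The point holds as a modest efficiency improvement, not as an error in the plan. The SAP relies on baseline immunization for two subgroups and leaves it out of the primary model, and the quarter terms do not replace individual status. The primary test remains valid without it.

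The benefit of adding it is slightly less attenuation of the hazard ratio and correction of chance imbalance. That is worth about 0 to 2 power points if the immunization HR is 0.7 to 0.5, and about 4 to 5 points if it is 0.3. These figures rest on assumed vaccine effects and uptake, 1:1 allocation, a true dose HR of 0.80 and roughly 450 to 470 events. The omission itself is certain; its size is not.

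**What to change.** Optional and low priority. If the study is still blinded:

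- Add baseline immunization to the covariates of the primary model, the secondary model (non-Hispanic White participants at or above 40.0 degrees) and the time-varying model.
- Code it as none, partial or full. Full follows the SAP's existing definition; partial is any dose short of it. This coding rule is new and must be written down.
- Add it to the imputation model. This also covers missing values of a variable that defines two subgroups.
- Leave it out only within the two immunization subgroups, where it does not vary.

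The cost is a short SAP change, the partial-immunization rule and one covariate beyond the list mirrored from the earlier trial. It presumes that the variable was collected, as the subgroups imply. If it fails proportional hazards, the SAP's rule of stratifying on the failing variable already applies. If unblinding has taken place, keep the primary model as written and report the adjusted model as a labelled sensitivity analysis.
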